1 OBJECTIVES

- To determine the effect of nicotine salt (nicotine benzoate) and free-base nicotine in different flavored e-liquid solutions on puffing behaviors and systemic exposure to nicotine from ENDS by 1) Assessing short-term effects on nicotine cravings, withdrawal, and satisfaction from single use of ENDS refilled with flavored nicotine salt or flavored free-base nicotine solutions with two different flavors (tobacco or unflavored) in current daily ENDS users following an overnight fast; and 2) Comparing users' perceptions and preferences towards inhaling vapors containing nicotine salt (nicotine benzoate) or free-base nicotine with two different flavors (tobacco and unflavored) versus their regular brand.
- This project provides important information on whether the pharmacokinetics of nicotine delivery differ between salt and free-base forms of e-liquid of equivalent nominal concentration using the same device, and whether the previously observed effects of flavors on subjective effects differ between salt and free-base forms.

1.1 Primary Objective(s)

- Determine whether C_{max} or T_{max} differ between free-base and salt-based versions of the same liquid, controlling for flavoring and nominal nicotine concentration [main effect of salt]
- Determine whether the effect of flavoring on subjective effects (e.g., harshness, liking) differs between matched free-base and salt-based e-liquids [flavor X salt interaction]

1.2 Exploratory Objective(s)

[figure not shown]
- Examine effects of salt and flavoring on abuse liability using the Experimental Tobacco Marketplace (ETM).

2 BACKGROUND

Over the last 10 years electronic cigarettes also known as electronic nicotine delivery systems (ENDS) have gained considerable popularity especially among youth. Although definitive data are lacking, nicotine from ENDS is likely absorbed through the upper aero-digestive tract through mucosal surfaces or lung parenchyma that are in direct contact with ENDS aerosol. ENDS design has evolved over the past few years, from the small vaporizers that resembled conventional tobacco cigarettes ("cig-a-likes") to larger tank systems ("mods"). "Pods," the newest generation of ENDS, have soared in popularity in the past year, most notably, one brand, Juul. As of first quarter 2018, (per Nielson data) Juul had more than 50% of the ENDS market share, surpassing all of big tobacco's e-cigarette products together. Use of Juul products ('juuling') among youth has raised significant concern. All pod devices have a simplistic compact design and features that make them lightweight, ultra-portable and easy to use inconspicuously, with many simply resembling a computer thumb drive.

Each pod holds **nicotine salt** solution. Although the exact physiological mechanisms of nicotine salts have not been studied in detail, these compounds are believed to increase the amount and rate of nicotine uptake in pod users, effectively increasing the dose of nicotine delivered to the circulation and central nervous system. Modification of physicochemical properties of tobacco products to increase its addictiveness and appeal to users is not a new approach: Tobacco

companies have been known to add ammonia to tobacco to enhance nicotine's bioavailability to smokers. In addition to their potentially increased bioavailability, nicotine salts appear to be easier to inhale, as users report less upper respiratory tract irritation when compared with other products containing high nicotine concentrations. While youth don't identify nicotine as a reason for choosing ENDS products (indeed, youth often don't know which products do and don't contain nicotine), nicotine likely plays a determining role in the continued teen use of ENDS. Pods contain solutions with highly concentrated nicotine salts, primary nicotine benzoate.

PILOT STUDIES: We measured total nicotine concentration in pod products, and found that all tested products contained high nicotine concentrations, varying from 22 to 59 mg/mL (1). These concentrations are much higher than reported in older ENDS products. We also measured total nicotine yields in aerosols generated from these products using a smoking machine and standardized laboratory puffing protocol. We estimated that users of prefilled pod systems (e.g. Juul) may inhale with 10 puffs from 0.77 to 0.85 mg of nicotine (1). This estimated nicotine dose is higher than previously reported in older generations of EC devices (0.02–0.51 mg/10 puffs) (2).

JUUL has emerged as the leading mass-marketed vaping product over the last year, and other manufacturers have commenced selling salt-based liquids. There is emerging evidence suggesting that this form of nicotine delivery allows for higher nominal concentrations to be combined with lower heating temperatures for aerosol generation to provide less perceived harshness and fewer volatile organic compounds on a per-unit-nicotine basis. However, the pharmacokinetics of nicotine delivery for salt-based liquids has not been fully elucidated, and it is unclear whether the salt *per se* affects absorption, subjective effects, or product choice under standardized conditions of use. Similarly, while anecdotal evidence from users suggests that JUUL-like products are perceived as less harsh, there is little evidence from controlled studies. There is also limited evidence from food research that sodium benzoate, the salt used in JUUL and other salt-based liquids, may enhance sweet tastes and suppress bitter tastes. So, salts may have additional effects on flavor perceptions. Understanding pharmacokinetics and subjective effects is crucial to understanding whether salt-based liquids differ from other e-liquids in terms of abuse liability. Behavioral economics provides additional insights into abuse liability, particularly with regard to appeal and substitution, which can be assessed with the Experimental Tobacco Marketplace (ETM) (3). The ETM, combined with PK and subjective effects data, can provide layers of insight into the abuse liability of salt-based flavored ENDS.

3 INCLUSION AND EXCLUSION CRITERIA

Screening: Upon calling, potential participants will be given a brief explanation of the study and their eligibility to participate will be determined (**Appendix D:** Telephone Screening Questionnaire). All participants who meet the inclusion and exclusion criteria summarized in **Section 3.1** and **Section 3.2** will be treated on an outpatient basis.

All four study visits will take place in the Department of Health Behavior - Human Exposure Lab at Roswell Park Comprehensive Cancer Center (Basic Science Bldg. Room 3920). The laboratory is 10'10.5" x 11'8" space equipped with a sink, multiple infusion chairs, and an Axis Communications video camera. In addition, the laboratory also has a specialized mechanical exhaust system designed to keep the room under negative air pressure at all times.

In order to minimize any carry-over effect, there will be a minimum 5-7-day wash-out period between each scheduled study visit and, the order of the e-liquid flavors will be randomly assigned.

3.1 Inclusion Criteria

- Age \geq 21 years and \leq 55 years
- Willingness to abstain from using ENDS product for 8-10 hours (overnight abstinence) prior to study visits
- Current daily ENDS user as determined by
 - Has used ENDS product every day for the past 6 months (by history)
 - Has used ENDS product or e-liquid containing nicotine (by history)
- Participant must understand the investigational nature of this study and sign and Independent Ethics Committee/Institutional Review Board approved written informed consent form prior to receiving any study related procedure.

Refer to **Appendix A** for the Investigator Study Eligibility Verification Form: Inclusion Criteria.

3.2 Exclusion Criteria

- Smoked cigarettes in the past 7 days.
- Currently smokes \geq 5 cigarettes per month.
- Unstable medical conditions (such as unstable heart disease, uncontrolled hypertension, thyroid disease, diabetes, renal or liver impairment, or glaucoma) or psychiatric condition (such as current major depression, history of schizophrenia or bipolar disorder) or current regular use of psychiatric medications (such as major tranquilizers and antidepressants).
- History of serious side effects from nicotine or from any nicotine replacement therapies.
- Uncontrolled intercurrent illness including, but not limited to, ongoing or active infection, symptomatic congestive heart failure, unstable angina pectoris, cardiac arrhythmia, or psychiatric illness/social situations that would limit compliance with study requirements.
- Pregnant or nursing females.
- Concurrent participation in another clinical trial

Roswell Park Protocol No.: I 475819

- Unwilling or unable to follow protocol requirements.
- Any condition which in the Investigator's opinion deems the participant an unsuitable candidate.

Refer to **Appendix B** for the Investigator Study Eligibility Verification Form: Inclusion Criteria.

3.3 Inclusion of Women and Minorities

Both men and women and members of all races and ethnic groups are eligible for this study.

3.4 Special Populations

The following special populations are excluded from this study:

- Cognitively impaired adults/adults with impaired decision-making capacity
- Individuals who are not yet adults (infants, children, teenagers)
- Pregnant women
- Prisoners

4 LOCAL AND STUDY-WIDE NUMBER OF SUBJECTS

This is a single center study to be conducted at Roswell Park. The target accrual is 20 evaluable participants (participants who have completed all 4 study visits), with an equal number of males and females. Accrual is expected to take up to 4 years.

5 LOCAL AND STUDY-WIDE RECRUITMENT METHODS

Participants will be recruited from advertisements in local newspapers/magazines, posters, community centers, churches, and from several websites (Roswell websites, Craigslist.org, Facebook, and Instagram). An example of the participant recruitment material can be found in **Appendix C**. Applicants will be invited to call a local number. On calling, applicants will be given a brief explanation of the study and their eligibility to participate will be assessed (**Appendix D**). Those who meet eligibility criteria will be included in the study and attend 4 weekly sessions. We anticipate that each session will take 120 minutes. After completion of each visit, participants will be asked to vape as usual over the next week, and the procedures will be repeated every week for the total of 4 visits.

Study participants will be compensated by cash for each study visit completed and will receive additional "bonus" cash if all study visits have been completed. Payments will be disbursed according to the following schedule (**Table 1**):

Table 1 Study Payment Schedule

Study Visit	Payment Amount
1	\$50.00
2	\$60.00
3	\$70.00
4	\$80.00
All Visits Completed	\$90.00 bonus
TOTAL	\$350.00

6 MULTI-SITE RESEARCH

- Not Applicable – This is a single-site study.

7 STUDY TIMELINES

- The anticipated duration of intervention is 4 weeks. Each participant will be scheduled for 4 study visits. Study visits may occur at a minimum of 5-7 days apart, but no more than 4 weeks apart.
 - Each study session is expected to take approximately 2.0 to 2.5 hours.
 - The duration anticipated to enroll all study participants is 4 years.

8 STUDY ENDPOINTS

8.1 Primary Endpoint(s)

- Maximum concentration of nicotine in plasma (C_{max}), the area under the concentration – time curve from 0 to 120 min (AUC), and the time to maximum concentration (T_{max}).

8.2 Secondary Endpoint(s)

- Perceived harshness, satisfaction, liking, and relief of nicotine withdrawal symptoms.

8.3 Exploratory Endpoint(s)

- Demand indices including intensity and elasticity of demand for each device sampled and substitution levels of alternative tobacco products.

9 DESIGN

This is a single center, randomized, double blind clinical trial pilot. Using a 2 (free-base vs salt) x 2 (tobacco vs unflavored) factorial design, 20 current daily vapers will be asked to use one of four liquids across four 2.5-hour laboratory sessions. The order of the tested conditions will be randomized and study personnel as well as participants will be blinded to the four liquids throughout the study. Participants will be aged 21-55, use a vaping product daily, have a preferred flavor of tobacco, and not currently smoke cigarettes (no cigarette use in the past seven days and no more than 5 cigarettes in last 30 days). For each session, participants will arrive after overnight abstinence and be randomly assigned to one of the four liquids and puff according to a standardized protocol (10-minute bout, 20 puffs, 30 second inter-puff interval). Venous blood samples (4 mL) to measure nicotine will be drawn by a either certified phlebotomist through a butterfly needle or

Roswell Park Protocol No.: I 475819

through a catheter by a certified registered nurse before and at 2, 4, 5, 6, 8, 10, 13, 15, 20, 30, 45, 60, 90, and 120 min after onset of use. Samples will be processed within 2 hours and frozen at -80°C until analysis. Plasma samples will be analyzed for nicotine concentration using sensitive and validated UPLC-MS/MS method developed by TCORS analytical core located at Roswell Park. At the same time intervals, participants will complete standard subjective effects measures, including the Drug Effects scale, ENDS Nicotine Dependence Scale, Minnesota Nicotine Withdrawal Scale, Product Evaluation Scale, and the Duke Sensory questionnaire, Delay Discounting Task and the ETM with the product being tested available for the fixed price in the marketplace. Participants will be compensated by cash for each study visit completed and will receive an additional \$90.00 bonus if all study visits have been completed (**Table 1**).

10 INTERVENTION

Active Substance and Source

During each visit, following an overnight abstinence, participants will be asked to take 20 puffs over 10 minutes (one puff every 30 seconds) from an Innokin EQs Ultra-Compact 2 mL Refillable Pod Vaporizer equipped with a 800mAh battery. All devices and solutions will be purchased from a local vape shop called the House of Vapor located in Kenmore, NY. Study personnel will set the device to 11.5W for every study session.

10.1 Dosing and Administration

The device will be filled with either (1) free-based nicotine e-liquid solution of unflavored (2) free-based nicotine e-liquid solution of tobacco flavor (3) salt-based nicotine e-liquid solution of unflavored or (4) salt-based nicotine e-liquid solution of tobacco flavor. Both the study personnel and study participants will be blinded to the solution flavor and nicotine concentration. All e-liquids will contain 0.148M nicotine (24 mg/mL free-base nicotine or 24 mg/mL nicotine benzoate). Participants are randomized to the order of the e-liquids by the study statistician using the Williams Design; a special case orthogonal latin squares design generated using SAS v9.3.

Intervention will be administered on an outpatient basis. Reported adverse events (AEs) and potential risks are described in **Section 13** and **Section 17**.

Nicotine (3-(1-methylpyrrolidin-2-yl)-pyridine) the primary alkaloid in tobacco products binds stereo-selectively to nicotinic-cholinergic receptors on autonomic ganglia, the adrenal medulla, neuromuscular junctions and in the brain. Nicotine exerts two effects, a stimulant effect exerted at the locus ceruleus and a reward effect in the limbic system. Intravenous administration of nicotine causes release of acetylcholine, norepinephrine, dopamine, serotonin, vasopressin, beta-endorphin and ACTH. Nicotine is a highly addictive substance. Nicotine also induces peripheral vasoconstriction, tachycardia and elevated blood pressure. Nicotine replacement therapies (like inhalers and patches) are used to treat smoking withdrawal syndrome. Nicotine is classified as a stimulant of autonomic ganglia.

Electronic nicotine delivery systems (ENDS) usually look similar to regular cigarettes, cigars, pipes, or pens, but do not contain tobacco. Instead, they are comprised of a battery-powered atomizer that produces vapor for inhalation from solutions that contain nicotine. Electronic cigarettes (e-cigarettes) are the most popular ENDS on the market. Different ENDS brands are engineered differently. The differences include the appearance, the nature of nicotine solution, the capacity of the cartridge containing the solution, the nature of the heating element, and size and

Roswell Park Protocol No.: I 475819

type of battery. Propylene glycol or glycerin, are primary used as solvents for nicotine. Solutions may contain just one or both solvents mixed with water. Various additives and flavorings are commonly added to nicotine solution, including fruit and candy flavors, ethyl alcohol, non-nicotine pharmacologically active compounds and stabilizers. ENDS devices of newer generation often contain nicotine salt solution. Although the exact physiological mechanisms of nicotine salts have not been studied in detail, these compounds are believed to increase the amount and rate of nicotine uptake in pod users, effectively increasing the dose of nicotine delivered to the circulation and central nervous system. The heating elements are usually thin (filament) wire made with various metals (nickel, chromium, copper coated with silver). These engineering features affect the chemical composition of the ENDS vapor. The type of ENDS and e-liquid solution that will be provided to study participants includes:

Table 2.

ENDS and E-liquid Solutions

Innokin EQs Ultra-Compact Refillable Pod Vaporizer ¹	
Free-based nicotine solution Unflavored (24 mg/mL)	
Free-based nicotine solution Tobacco (24 mg/mL)	

Salt-based nicotine solution Unflavored (24 mg/mL nicotine benzoate)	
Salt-Based solution Tobacco (24 mg/mL nicotine benzoate)	

1 ENDS used at all 4 study visits

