32 DRUGS OR DEVICES

During each visit, participants will be asked to take 20 puffs over 10 minutes (one puff every 30 seconds) from an Innokin EQs Ultra-Compact 2 mL Refillable Pod Vaporizer equipped with a 800mAh battery (**Table 2**). Study personnel will set the device to 11.5W at every study session. The device will be filled with either (1) free-based nicotine e-liquid solution of unflavored (2) free-based nicotine e-liquid solution of tobacco flavor (3) salt-based nicotine e-liquid solution of unflavored or (4) salt-based nicotine e-liquid solution of tobacco flavor. Both the study personnel and study participants will be blinded to the solution flavor and nicotine concentration.

All e-liquids will contain 0.148M nicotine (24 mg/mL free-base nicotine or 42 mg/mL nicotine benzoate).

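### The salt liquids are 24 mg/mL nicotine benzoate in Section 10.1 and Table 2 but 42 mg/mL in Section 32; read as salt mass, only 42 mg/mL is 0.148 M, so confirm the nicotine content and align the text

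*Combined protocol and SAP*

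**What the plan says.** Section 10.1 sets one molarity for all four liquids and gives it in mass terms: "All e-liquids will contain 0.148M nicotine (24 mg/mL free-base nicotine or 24 mg/mL nicotine benzoate". Table 2, in the same section, carries that strength in both salt rows: "Salt-based nicotine solution Unflavored (24 mg/mL nicotine benzoate" and "Salt-Based solution Tobacco (24 mg/mL nicotine benzoate". Its two free-base rows also read 24 mg/mL.

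Section 32 has the same sentence with a different salt figure: "All e-liquids will contain 0.148M nicotine (24 mg/mL free-base nicotine or 42 mg/mL nicotine benzoate".

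The Objectives (Sections 1 and 1.1) and the primary analysis (Section 19.4) compare salt with free base at the same nominal nicotine strength. Section 19.2 gives a single strength of about 24 mg, without a volume or chemical form. Section 10 says the liquids are bought from a local vape shop.

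**The concern.** The protocol gives two strengths for the same salt liquids, and nothing marks either as superseded. A salt is the base plus its acid, so a mole of it weighs more than a mole of the base. If each mg/mL figure is the mass of the substance named beside it, 24 mg/mL cannot describe both forms at one molarity.

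This is the dose specification for the primary comparison. The Section 19.4 model contains base, flavor, their interaction, the prior combination and a random subject effect. Nicotine concentration is held equal only by the liquids themselves. If the salt liquids were weaker, every salt session would be a lower-concentration session, and no model term could separate the two effects. A weaker salt liquid would also work against finding the greater uptake that the Background says salts are believed to give.

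Session staff would not be expected to notice: "Both the study personnel and study participants will be blinded to the solution flavor and nicotine concentration".

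**Working it through.** **Inputs.** The strengths 0.148 M, 24 mg/mL and 42 mg/mL come from Sections 10.1 and 32. Section 10.1 identifies the base by its chemical name, "Nicotine (3-(1-methylpyrrolidin-2-yl)-pyridine) the primary alkaloid in tobacco products", which fixes the formula C10H14N2. The documents print no molar masses; those below use standard atomic weights (C 12.011, H 1.008, N 14.007, O 15.999).

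- Nicotine: 10 × 12.011 + 14 × 1.008 + 2 × 14.007 = 162.24 g/mol
- Benzoic acid, C7H6O2: 7 × 12.011 + 6 × 1.008 + 2 × 15.999 = 122.12 g/mol
- 1:1 nicotine benzoate: 162.24 + 122.12 = 284.36 g/mol

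**Formula.** Molarity = (mg/mL) ÷ (g/mol).

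**The plan's own figure.** Free base: 24 ÷ 162.24 = 0.148 M. This reproduces.

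**Salt at the Section 32 figure.** 42 ÷ 284.36 = 0.148 M. Nicotine content is 0.1477 × 162.24 = 24.0 mg/mL. This also reproduces and matches the free-base liquid.

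**Salt at the Section 10.1 and Table 2 figure, read as salt mass.** 24 ÷ 284.36 = 0.0844 M. Nicotine content is 0.0844 × 162.24 = 13.7 mg/mL, and 13.7 ÷ 24 = 57% of the free-base strength, a shortfall of 43%.

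**Rounding.** Over 0.1475 to 0.1485 M, the required salt mass is 41.9 to 42.2 mg/mL, so rounding does not explain 24.

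**Stoichiometry.** A 1:2 salt would be 162.24 + 2 × 122.12 = 406.48 g/mol. At 24 mg/mL it would be 0.059 M (9.6 mg/mL nicotine, 40%), at 42 mg/mL it would be 0.103 M, and 0.148 M would need 60.2 mg/mL. Only the 1:1 salt agrees with Section 32.

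**Check from the documents alone.** The stated figures imply molar masses of 24 ÷ 0.148 = 162.2 and 42 ÷ 0.148 = 283.8 g/mol, in line with those used above. If 42 mg/mL of salt carries the intended nicotine, 24 mg/mL of salt carries 24 ÷ 42 = 57% of it.

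**Alternative reading.** If 24 mg/mL means 24 mg/mL of nicotine present as benzoate, the salt liquid is 24 ÷ 162.24 = 0.148 M and the four liquids match.

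**The case against.** The strongest reply is that 24 mg/mL is a nicotine-equivalent strength. Sections 10.1 and 32 both state 0.148 M for every liquid, Section 32 supplies the matching salt mass, the objectives call for equal nominal strength, and Section 19.2 gives one strength for all cartridges. The Background pilot work also reports pods by total nicotine: "We measured total nicotine concentration in pod products". For the salt to have been weaker, all of this would have to have been ignored when the liquids were obtained. On this reading only the wording is wrong.

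Most of that stands, and it makes a specification error the likelier explanation. It also means that 24 mg/mL fails to equal 0.148 M only when read as salt mass. It does not close the question, because Section 10.1 and Table 2 name nicotine benzoate, Section 32 expresses the salt as salt mass, and Section 19.2 names neither volume nor form.

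Section 13 refers to laboratory testing of nicotine yields before human use, which might have exposed a shortfall, but no result is given for these four liquids. The 20-puff yield in Section 11 (1.5 to 1.7 mg) does not verify them either. It is twice the Background estimate that users of "prefilled pod systems (e.g. Juul) may inhale with 10 puffs from 0.77 to 0.85 mg of nicotine" (2 × 0.77 = 1.54; 2 × 0.85 = 1.70), so it appears to describe other products.

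A reader might infer that participants received a weaker salt liquid, or that the salt contrast is already biased. The documents support neither inference. They show a conflict in the specification and contain no measurement of the liquids.

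**Conclusion.** The inconsistency is real and should be fixed. Section 10.1 and both salt rows of Table 2 conflict with Section 32, and read as salt mass only 42 mg/mL of the 1:1 salt matches 0.148 M.

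The consequence depends on a fact that the documents do not give:

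- If 24 mg/mL is nicotine equivalent, there is no bias and only the text needs correcting. This is the likelier case.
- If 24 mg/mL is salt mass, the salt liquids hold 13.7 mg/mL nicotine, 57% of the free-base strength, and the AUC and Cmax contrast cannot separate salt form from concentration.

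The figures assume a 1:1 salt and standard atomic weights. Confidence is high for the mismatch in the text. Whether a weaker liquid was bought is unknown; it is a risk to rule out.

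**What to change.** 1. Have someone outside the blinded session staff confirm and record the nicotine content of all four liquids against 0.148 M. The source must say whether the figure is nicotine or salt mass, so use a supplier specification or an assay. A label reading only 24 mg/mL would leave the same ambiguity.
2. If the liquids are equimolar, change Section 10.1 and both salt rows of Table 2 to: *42 mg/mL nicotine benzoate (equivalent to 24 mg/mL nicotine, 0.148 M)*. This agrees with Section 32.
3. If they are not, replace unused liquids with 0.148 M liquids, report the actual strengths of any already used, and do not attribute the AUC or Cmax difference from those sessions to salt form.

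Dose-normalising AUC and Cmax by liquid concentration would not rescue affected sessions. The protocol fixes puff number and spacing but not puff volume, and topography is monitored only in a later ad lib bout (Section 11), so liquid concentration is not delivered dose. Section 11 also allows for baseline nicotine above its abstinence cut-off, and dividing by concentration would wrongly rescale that baseline.

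The cost is a specification request or assay for four liquids and a wording change in Section 10.1, including Table 2. If the liquids are equimolar, sample size, visits and model are unchanged.
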